1. SYNOPSIS

Study Title	Administration of ondansetron with P-glycoprotein inhibitor tariquidar in patients with neuropathic pain
Objective	To determine the pharmacokinetics and tolerability of co-administration of 5-HT ₃ R antagonist ondansetron with a P-glycoprotein inhibitor tariquidar, in patients with neuropathic pain.
Hypothesis	Co-administration with tariquidar will increase the cerebrospinal fluid (CSF) to plasma ratio of ondansetron after intravenous administration. Co-administration of a single dose 16mg ondansetron with 4mg/kg tariquidar will be tolerable in patients with neuropathic pain
Study Period	Planned enrollment duration: Approximately 24 months Planned study duration: Approximately 30 months
Number of Subjects	28 evaluable patients with peripheral neuropathic pain
Study Drug	Two infusions of 16mg intravenous ondansetron co-administered with intravenous 4mg/kg tariquidar or placebo (D5W), 3 weeks apart. If intolerable, the dose of ondansetron will be reduced to 12mg or 8mg in a stepwise fashion (see section 3.2).
Study Design	Prospective, randomized, double-blind, placebo controlled, cross-over proof of concept study.

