In addition, a series of experiments were performed to determine the concentration of ondansetron in rat CSF, spinal cord, and brain, performed in wild-type rats, with and without intravenous 7.5mg/kg tariquidar co-administration.

- Plasma to CSF partition coefficient (Cp) of ondansetron, after 10mg/kg dose, in wild-type male rats without tariquidar was 0.27 ± 0.3 ; plasma to CSF partition coefficient (Cp) of ondansetron, with co-administration of 7.5mg/kg tariquidar was 0.36 ± 0.16
- Plasma to spinal cord partition coefficient (Cp) of ondansetron, after 10mg/kg dose, in wild-type male rats without tariquidar was 1.11 ± 0.4 ; plasma to spinal cord partition coefficient (Cp) of ondansetron with co-administration of 7.5mg/kg tariquidar was 4.72 ± 2.8
- Plasma to brain partition coefficient (Cp) of ondansetron, after 10mg/kg dose, in wild-type male rats without tariquidar was 1.75 ± 1.2 ; plasma to brain partition coefficient (Cp) of ondansetron with co-administration of 7.5mg/kg tariquidar was 5.88 ± 5.6

In summary, co-administration of tariquidar resulted in 1.3 fold increase in CSF to blood partitioning coefficient, while in parallel, spinal cord to blood partitioning coefficient increased 4.2-fold, and brain to blood partitioning coefficient increased by 3.4-fold.

Cardiovascular safety data from the first 8 participants in the human pharmacokinetic study per IND 140361 (NCT03809234; 2 participants with 4mg ondansetron, 4 participants with 8mg ondansetron, and 2 participants with 16 mg ondansetron, with and without 4mg/kg tariquidar) demonstrate the following:

- None of the participant had any increase in troponin at any point in the study.
- The QTc interval changes (before to after ondansetron) with and without tariquidar were -2.5 ± 16.1 ms vs 2.9 ± 13.1 ms, respectively (non-significant difference).
- Maximum change in systolic blood pressure was an 8.6 ± 9.7 mmHg increase, two hours after infusion of ondansetron with placebo, and a 5.7 ± 8.2 mmHg decrease, 1.5 hours after infusion of ondansetron with tariquidar, across doses.
- Maximum change in diastolic blood pressure was an 3.4 ± 7.7 mmHg increase, two hours after infusion of ondansetron with placebo, and an 7.1 ± 9.6 mmHg increase, 105 minutes after infusion of ondansetron with tariquidar, across doses.

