2.4.5 Observations and Measurements

2.4.5.1 Primary Outcome Measures

Primary outcome:

The primary objectives are to evaluate the pharmacokinetics and the tolerability of ondansetron and tarividar single dose iv co-administration (in comparison to ondansetron administration alone) in patients with neuropathic pain.

Pharmacokinetics:

-Venous blood sampling for pharmacokinetics will be obtained: at 0, 15, 30, 60, 90, 120, 180, and 240 minutes from the beginning of ondansetron infusion.

-A CSF sample will be obtained via lumbar puncture between 30 and 180 minutes from the beginning of ondansetron infusion, for the assessment of ondansetron concentration in the CSF using population PK approach.

-CSF to plasma ratio of ondansetron will be calculated, and compared between the two study arms

Tolerability:

-Spontaneous reporting of adverse effects

- Vital signs (pulse oximetry, blood pressure): before infusion and 30, 60, 120, 180 and 240 minutes after end of ondansetron infusion.
- 12-lead ECG: At baseline and prior to discharge after each treatment session.
- Troponin T: at screening and prior to discharge after each treatment session.
- Blood chemistry (CMP) and count (CBC) at baseline and at 3-week time point after each treatment session.
- In patients who are concomitantly treated with SSRI or SNRI medications that are allowed for inclusion (duloxetine ≤60mg/day, citalopram ≤20mg/day, or Escitalopram ≤10mg/day, additional assessments will be performed at the time of vital sign assessments (baseline and 30, 60, 120, 180 and 240 minutes after end of ondansetron infusion) to evaluate confusion, restlessness, dilated pupils, muscle twitching or rigidity, and sweating. This will be performed to identify signs suggestive of serotonin syndrome.

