2.4.7 Statistical Methods

All demographic, sensory, analytical and patient-reported data will be captured on case report forms, manually entered to a Research Electronic Data Capture (REDCap) database that will be created for the project, and will be verified by an independent study team member. Plasma and CSF concentrations of ondansetron will be analyzed using a previously validated liquid chromatography method.³⁹ Non-compartmental PK analysis will be performed to construct the concentration-time curves of ondansetron in human plasma with and without tariquidar.³¹ Ondansetron concentration in CSF will be used to evaluate biodistribution of ondansetron to CNS, by the means of CSF to plasma concentration ratio. We do not expect missing outcomes data as all primary and most secondary outcomes will be collected with the participants physically present with the research team. Any missing data will be described, but no data imputation will be attempted. Intergroup comparisons for parametric data will be performed by paired t-test, and for non-parametric data by Wilcoxon signed-rank test for paired samples. McNemar's test will be used to compare paired nominal data, and Fisher's exact test to compare non-paired nominal data.

Sample size:

Change in spontaneous pain reduction (secondary outcome) was used to determine the sample size for the study. The baseline pain intensity (\pm SD) of patients with peripheral neuropathy we have recruited to various studies over the past two years have been 6.3 ± 2.1 . This proof of concept study expects to demonstrate a 30% difference in pain reduction between the two intervention sessions. Given that in a published study of IV ondansetron in NeuP a 20% pain reduction has been observed (although not different from placebo), we assume pain intensity of 5.1 ± 2.1 in ondansetron+placebo group, and expect pain intensity of 4.0 ± 2.1 in ondansetron+tariquidar group at the 60-120 minute timeframe. To determine a significant difference with two-tailed $\alpha < 0.05$ and 85% power (effect size 0.52), 28 subjects will be required in this cross-over study. We expect to enroll 28-32 participants to the study to reach 28 evaluable participants.

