3.2 Dose Limiting Toxicities

The dose-limiting toxicities (DLT) for the study are defined as follows:

- New QTc prolongation >60ms greater than baseline, or QTc>450ms
- Troponin T elevation > 0.03 ng/mL
- Syncope
- Sustained increase or decrease in SBP of >30 mmHg systolic or >20 mmHg diastolic
- Sustained vital sign abnormalities
 - HR<40 or >120 beats per minute
 - SpO2 <92%

- ALT/AST \geq 3xULN AND total bilirubin \geq 2xULN
- AST/ALT \geq 8xULN
- Altered mental status (delirium, inability to follow simple commands)
- Persistent visual disturbances

If DLT is observed in >2 participants, ondansetron dose will be reduced to 12 mg for all new participants.

If further DLT is observed in >2 participants receiving 12 mg ondansetron, the dose will be reduced to 8 mg for all new participants.

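### Comparative tolerability is a primary outcome, but section 2.4.7 offers only tests of no difference, with no interval or bound; at 28 pairs a sizeable excess of adverse events can be non-significant

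*Combined protocol and SAP*

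**What the plan says.** The synopsis states the second hypothesis as "Co-administration of a single dose 16mg ondansetron with 4mg/kg tariquidar will be tolerable in patients with neuropathic pain". Section 2.4.5.1 makes tolerability a primary objective alongside pharmacokinetics, and makes it comparative: "single dose iv co-administration (in comparison to ondansetron administration alone) in patients with neuropathic pain". The tolerability measures listed there are reported adverse effects, vital signs, 12-lead ECG, troponin and blood chemistry and counts.

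Section 2.4.7 is the only statistical methods section. For continuous data it says "Intergroup comparisons for parametric data will be performed by paired t-test, and for non-parametric data by Wilcoxon signed-rank test for paired samples". For categorical data it says "McNemar's test will be used to compare paired nominal data, and Fisher's exact test to compare non-paired nominal data". These are general statements and no tolerability variable is assigned to a test. The section gives no confidence interval, upper bound or criterion for tolerability, and it sets the sample size of 28 on pain, a secondary outcome.

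Elsewhere there are count rules. Section 3.2 lists dose-limiting toxicities (DLTs) and says "If DLT is observed in >2 participants, ondansetron dose will be reduced to 12 mg for all new participants"; the synopsis points to this section when it speaks of intolerability. Section 3.4 sets an early stopping criterion at more than 7 participants meeting the withdrawal criteria. Section 2.3.1 recruits until 28 participants have completed both sessions, section 3.3 replaces those who withdraw, and section 2.4.7 rules out imputation.

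**The concern.** A hypothesis that a treatment is tolerable is a claim that any added harm is small. A test of no difference cannot support that claim when it fails to reject; only an estimate with a bound can. With 28 pairs, failure to reject is compatible with an excess of harm that a clinician might well care about. If the report gives only p-values, a reader could take a non-significant one as support for the hypothesis. Section 2.2 says tolerability in these patients should be evaluated before large efficacy studies, so that is the decision at stake.

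A second weakness concerns who is counted. Nearly every DLT in section 3.2 is also a withdrawal criterion in section 3.3. A participant withdrawn after an event in session 1 is replaced and may never form a pair, so a paired test in completers could leave out the people who were harmed.

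**Working it through.** **Inputs.** 28 pairs, two-sided 0.05 (section 2.4.7); pilot QTc-change SDs of 16.1 and 13.1 ms (section 2.2); the thresholds of more than 2 and more than 7 participants (sections 3.2 and 3.4). The plan gives no sample size, power or precision for tolerability, so there is no figure of its own to reproduce. The documents give no expected adverse event rates or within-person correlation; those below are assumptions.

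**1. What McNemar's test can miss.** Let b be participants with an event only in the tariquidar session and c those with one only in the placebo session. The plan does not say which version of the test it means. Exact two-sided p = 2 × P(X ≤ c), X ~ Binomial(b+c, 0.5). Uncorrected: χ² = (b−c)²/(b+c), 1 df. Excess = (b−c)/28.

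| b v c | Excess | Exact p | Uncorrected p |
|---|---|---|---|
| 3 v 0 | 3/28 = 11% | 2×0.5³ = 0.25 | χ²=3.00, 0.083 |
| 5 v 0 | 5/28 = 18% | 2×0.5⁵ = 0.0625 | χ²=5.00, 0.025 |
| 6 v 0 | 6/28 = 21% | 2×0.5⁶ = 0.031 | χ²=6.00, 0.014 |
| 6 v 1 | 5/28 = 18% | 2×8/128 = 0.125 | χ²=25/7=3.57, 0.059 |
| 7 v 1 | 6/28 = 21% | 2×9/256 = 0.070 | χ²=36/8=4.50, 0.034 |

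The unstated choice of version decides 5 v 0 and 7 v 1.

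**2. Probability of missing a true excess.** This is full enumeration over 28 pairs. The independence columns take events in the two sessions as independent within a person. The nested columns assume that everyone who reacts on placebo also reacts on tariquidar.

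| Placebo v tariquidar rate | Exact, independent | Uncorrected, independent | Exact, nested | Uncorrected, nested |
|---|---|---|---|---|
| 0% v 15% | 76% | 38% | 76% | 38% |
| 5% v 15% | 92% | 78% | 94% | 69% |
| 5% v 20% | 78% | 62% | 76% | 38% |
| 5% v 25% | 61% | 45% | 50% | 16% |

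**3. QTc by paired t-test.** SD of the paired difference = √(16.1² + 13.1² − 2r×16.1×13.1), which is 20.8 ms at r=0 and 14.8 ms at r=0.5. From the noncentral t with 27 df, a true 5 ms increase is missed 77% (r=0) to 59% (r=0.5) of the time, and a 10 ms increase 31% to 7%. The half-width of a 95% interval would be 2.052 × 20.8/√28 = 8.0 ms to 2.052 × 14.8/√28 = 5.8 ms. The SDs come from 8 people pooled over 4, 8 and 16 mg, only 2 of them at 16 mg, so these figures are rough.

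**4. What an interval would show.** Tango 95% intervals for the paired risk difference at 28 pairs are −3% to 27% for 3 v 0, 3.6% to 35.6% for 5 v 0, and 2.0% to 40.9% for 7 v 1. The last two exclude zero although exact McNemar does not reject, because Tango's is a score interval. The interval method therefore has to be named in advance.

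For the rate in the tariquidar session, the exact one-sided 95% upper bound with no events is 1 − 0.05^(1/28) = 10.1%. The Clopper-Pearson bound is 15.9% for 1 of 28 and 20.8% for 2 of 28.

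**5. What the count rules would catch.** With 28 participants and a common DLT risk p, P(more than 2) is 54% at p=10%, 81% at 15% and 94% at 20%. P(more than 7 meeting withdrawal criteria) is 18% at a 20% risk.

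**6. Completers only.** As an illustration, suppose 2 participants have a DLT on tariquidar in session 1, are withdrawn and replaced, and the 28 completers have none. The paired table reads 0 v 0, while up to 30 people were dosed with tariquidar and 2/30 = 6.7% had a DLT.

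**The case against.** The strongest reply is that the documents never state the faulty inference. A reader might infer that the plan intends p>0.05 to mean tolerable. It does not say so: the sentence on McNemar's and Fisher's tests is a generic list. That reply stands, and the point is the absence of an interval or bound, not a stated wrong rule.

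Nor does the pilot QTc report, "were -2.5 ± 16.1 ms vs 2.9 ± 13.1 ms, respectively (non-significant difference", show that safety data are judged this way. It sits beside means and SDs, and section 2.2 draws no tolerability conclusion from it; it ends by saying that tolerability in patients is unknown.

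Sections 3.2 and 3.4, with the independent monitoring board in section 3.7, do give protection. At a 15% DLT risk the section 3.2 trigger is met 81% of the time, whatever McNemar's test shows. This stands and narrows the point. However, the rules count participants without separating the tariquidar from the placebo session, so they cannot give the comparison that section 2.4.5.1 asks for, and section 3.2 does not cover milder events.

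It is tempting to say that section 3.2 contradicts section 2.4.7, since three tariquidar-only DLTs trigger a dose reduction while 3 v 0 is non-significant. It does not: a precautionary count and a comparative test answer different questions. It would also be wrong to say that the comparison will almost always be non-significant. A 10 ms QTc increase is missed only 7% to 31% of the time.

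Finally, this is a proof-of-concept study and need not be powered for tolerability. That is fair, and it favours reporting precision over bare tests.

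**Conclusion.** The concern holds in this limited form. For a primary comparative question, section 2.4.7 offers only tests of no difference, and at 28 pairs these can be non-significant with an observed excess of 18 to 21 points (exact McNemar, 0 or 1 placebo-only events) or 11 to 18 points (uncorrected: 3 v 0, 6 v 1). Those thresholds are arithmetic and need no assumption beyond 28 complete pairs. The miss rates do rest on assumed event rates and on the within-person dependence shown; the QTc figures also rest on a very small, dose-pooled pilot.

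A non-significant result could be misread as support for tolerability; the documents do not plan that reading. The consequence lies mainly in the comparative estimate and in events below DLT grade. Restricting the comparison to completers could understate harm further. This should be corrected, but it does not undermine the design.

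**What to change.** In section 2.4.7, make estimation the basis of the tolerability conclusion:

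1. Among all participants dosed, report by session the proportion with any section 3.2 event and with any adverse event. Give the exact one-sided 95% upper bound for the tariquidar session.
2. In participants with both sessions, report the paired risk difference with a 95% confidence interval by one named method (for example Tango or Newcombe). Report mean paired differences in QTc, blood pressure and heart rate with 95% confidence intervals. Present these alongside the all-dosed results.
3. Keep p-values as descriptive, and name the version of McNemar's test. State that p>0.05 is not evidence of tolerability, and word the conclusion as the size of excess that the upper bound excludes.

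No change to the rules in sections 3.2 to 3.4 is proposed.

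The cost is a few sentences, with no new data, visits or participants. The downside is a less favourable safety statement: even 0 events in 28 leaves rates up to about 10% not excluded, and 2 in 28 leaves rates up to about 21%.

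### At the plan's own effect size of 0.52 and two-tailed 5% level, 28 pairs give about 76% power, not 85%; separately, the stated 30% difference does not match the pain values used

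*Combined protocol and SAP*

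**What the plan says.** Section 2.4.7 (Sample size) bases the number of participants on pain, not on a primary outcome: "Change in spontaneous pain reduction (secondary outcome) was used to determine the sample size for the study". Its inputs are:

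- Baseline pain in the group's earlier peripheral neuropathy patients: values "have been 6.3 ± 2.1".
- Target: the study "expects to demonstrate a 30% difference in pain reduction between the two intervention sessions". The base of the percentage is not defined.
- Ondansetron alone: in a published study "a 20% pain reduction has been observed (although not different from placebo"), from which "we assume pain intensity of 5.1" (SD 2.1) for the session with placebo.
- Ondansetron with tariquidar: the authors "expect pain intensity of 4.0 ± 2.1 in ondansetron+tariquidar group at the 60-120 minute timeframe".
- Error rates and result: two-tailed 5% level, 85% power, effect size 0.52, 28 participants in a cross-over design, with 28 to 32 enrolled to obtain 28 evaluable.

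Section 2.4.5.2 names the test for this outcome: a paired t-test, or the Wilcoxon signed-rank test if the data are not normal. Neither section gives the SD of the within-patient difference or the correlation between sessions.

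**The concern.** Two statements in the paragraph do not fit the numbers beside them. First, effect size, sidedness, power and sample size are all given, so each can be computed from the other three, and they do not agree. Second, the announced 30% difference cannot be recovered from 5.1 and 4.0.

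This calculation is the only justification given for 28 participants. If the pain comparison is null, a reader will take it that a 30% difference was sought with a 15% risk of missing it. On the plan's own effect size that risk is about 24%, and the difference sought was about 22% of the comparator score.

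**Working it through.** **Inputs** (all from section 2.4.7, except the test, from section 2.4.5.2): means 5.1 and 4.0; SD 2.1 per session; baseline 6.3; effect size 0.52; two-tailed 5%; n = 28; paired t-test.

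**Step 1. Where 0.52 comes from.** (5.1 − 4.0)/2.1 = 1.1/2.1 = 0.524, printed as 0.52. In a paired t-test the divisor is the SD of the difference, so the plan implicitly takes that SD as 2.1. If each session has SD 2.1 and the correlation is r, then

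SD of difference = 2.1 × √(2(1 − r)),

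which equals 2.1 when r = 0.5.

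**Step 2. Try to reproduce 28 for 85%.** Paired t-test power comes from the noncentral t distribution with n − 1 degrees of freedom and noncentrality d√n. With d = 0.52 and n = 28 the noncentrality is 0.52 × 5.292 = 2.75.

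| Test at 5% | Power at 28 pairs | Pairs for 85% |
|---|---|---|
| Two-sided, d = 0.52 | 75.6% | 36 |
| Two-sided, d = 0.524 | 76.2% | 35 |
| One-sided, d = 0.52 | 85.0% | 28 |

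The stated 28 and 85% reproduce only under a one-sided test. The normal approximation agrees on direction: ((1.960 + 1.036)/0.52)² = 33.2, so 34 pairs two-sided; ((1.645 + 1.036)/0.52)² = 26.6, so 27 one-sided. The two-sided shortfall is 85.0 − 75.6 = 9.4 percentage points.

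**Step 3. Sensitivity to the unstated SD** (difference 1.1, SD 2.1 per session, two-sided 5%, n = 28; the correlations are assumed):

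| r | SD of difference | Effect size | Power |
|---|---|---|---|
| 0.3 | 2.48 | 0.443 | 62% |
| 0.5 | 2.10 | 0.524 | 76% |
| 0.6 | 1.88 | 0.586 | 85% |
| 0.7 | 1.63 | 0.676 | 93% |

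Two-sided power of 85% with 28 pairs needs an effect size of 0.588, hence a correlation near 0.6.

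**Step 4. The 30%.**

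- Score relative to comparator: 1.1/5.1 = 21.6% lower.
- Reductions from baseline: (6.3 − 5.1)/6.3 = 19.0% and (6.3 − 4.0)/6.3 = 36.5%, a gap of 1.1/6.3 = 17.5 percentage points.
- Ratio of reductions: 2.3 against 1.2, which is 1.1/1.2 = 92% larger.

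None of these is 30%.

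**The case against.** The best defence on power is that the plan gives 2.1 as the SD of each session's score and never says it is the SD of the difference. With a correlation near 0.6, 28 pairs would reach 85% two-sided. That is possible in principle, but the effect size would then be about 0.59, and the plan prints 0.52. The plan cannot claim both. It is also true that up to 32 may be enrolled. Even if all 32 were evaluable, power at 0.52 would be 81.3%, and the plan counts on 28.

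Pain is a secondary outcome; sections 2.3 and 2.4.5.1 make pharmacokinetics and tolerability primary. That stands and limits the consequence.

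Stronger readings are tempting, but the documents do not support them:

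- *That 5.1 is an error and true power is 71%.* Since 6.3 × 0.8 = 5.04, a reader might put 5.04 in place of 5.1: 1.04/2.1 = 0.495 and power 71.4%. But 5.1 is a 19.0% reduction, is offered as an assumption, and lies within rounding: a baseline from 6.3125 up to 6.35 prints as 6.3, and 80% of it is 5.05 to 5.08. The substitution costs about 5 points (76.2% to 71.4%) and does not explain the shortfall of about 9 points already present at 0.52.
- *That the 30% mismatch itself means low power.* With SD 2.1, a score 30% below 5.1 (1.53 points) would give about 96% power at 28 pairs, and 30% of baseline (1.89 points) over 99%. A reduction 30% larger than 1.2 (0.36 points) would give about 14%. The mismatch leaves the target unclear; it does not settle the power.
- *That the authors ran a one-sided calculation.* The match with 28 is exact, but the text says two-tailed and shows no working. This is a likely explanation only.

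**Conclusion.** The point holds in two parts. First, the stated 85% is inconsistent with the plan's own effect size, sidedness, test and sample size: 28 pairs give about 76%, and 85% would take 36. This rests on normally distributed paired differences and on reading 0.52 as the paired effect size, meaning an SD of the difference of 2.1. Second, the announced 30% difference is not the effect used, which is 1.1 NRS points, or 21.6% below the comparator. This needs no assumption beyond the printed means.

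The effect is moderate: a type II error risk of about 24% instead of 15% for a secondary outcome. Nothing here bears on the pharmacokinetic or tolerability objectives, for which the paragraph makes no power claim.

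**What to change.** In the sample-size paragraph of section 2.4.7:

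1. Replace the 30% difference with the effect used: 1.1 NRS points, about 22% lower pain than with ondansetron plus placebo.
2. State the assumed SD of the within-patient difference (2.1, equivalent to a correlation of 0.5 if each session's SD is 2.1).
3. Restate two-tailed power at 28 evaluable participants as about 76%.

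If the sponsor has paired data supporting a correlation near 0.6, the alternative is to give that SD (about 1.88) and change the effect size to about 0.59; about 85% would then be consistent.

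The value 5.1 and the enrolment target can stay. Holding to 85% at 0.52 would need 36 evaluable participants, but a proof-of-concept study with pain as a secondary outcome can reasonably proceed with 28 if the power is reported correctly. The cost is a revision of one paragraph and a less favourable power figure.

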2.3.1 Subject Selection

Patients with neuropathic pain meeting inclusion criteria will be recruited from the Saint Louis community until 28 participants have completed both study sessions.

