2.4.5.2 Secondary Outcome Measures

Secondary outcome measures include:

1. Change in spontaneous pain intensity (measured on 0-10 NRS) from baseline to 60-120 minutes after ondansetron IV infusion, compared between two sessions with and without tariquidar. The pain severity values obtained at 60, 90, and 120 minutes will be averaged to derive the secondary outcome measure. The values will be compared via paired t-test (or Wilcoxon signed-rank test, if data not normally distributed).
2. Changes in NPSI total score and sub-scores (burning pain, paroxysmal pain, paresthesia/dysesthesia score) will be compared between treatment sessions;
3. The association between baseline Conditioned Pain Modulation (CPM) magnitude (Δ CPM) and the % pain reduction from baseline will be determined by bivariate regression. A significant association between the two measures will be indicative of differential analgesic response as a function of descending pain modulation;

Exploratory analyses will be performed to determine if variables such as sex, weight, baseline wind-up ratio (WUR), peak ondansetron plasma concentration, and P-glycoprotein genotype affect the difference in pain reduction between the two study sessions.

A population PK approach will be used to model CSF concentrations of ondansetron with and without tariquidar co-administration.

Table 1. Study Day Timeline

	Drug	Blood*		PK		NRS	NPSI	CPM	WUR	QST	Questionnaires
Screening	TQD	OND	X	Blood	CSF	X	X	X	X	X	X
Study day (min after ondansetron infusion start)											
Baseline			X	X		X	X	X	X	X	
-30 min	TQD / placebo Infusion										
0 min		OND infusion		X		X					
10 min						X					
15 min				X							
20 min						X					
30 min				X	X**	X					
40 min						X					
50 min						X					
60 min				X		X					
70 min							X				
75 min						X					
90 min				X		X					
105 min						X		X	X		
120 min				X		X					
135 min						X					

150 min						X					
165 min						X					
180 min				X		X					
240 min				X		X					
Hourly after discharge- study day						X					
Post-study day (weeks)											
1						daily					
2						daily					
3			X			daily					

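### With the stated two-tailed alpha of 0.05 and effect size 0.52, 28 participants give about 76% power, not 85%; the 85% figure matches a one-tailed test

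*Combined protocol and SAP*

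**What the plan says.** Section 2.4.7 states that "Change in spontaneous pain reduction (secondary outcome) was used to determine the sample size for the study". It takes a baseline pain of 6.3 (SD 2.1) from the group's earlier neuropathy patients. It then says "we assume pain intensity of 5.1 ± 2.1 in ondansetron+placebo group" and "expect pain intensity of 4.0 ± 2.1 in ondansetron+tariquidar group at the 60-120 minute timeframe". The conclusion begins "To determine a significant difference with two-tailed" alpha below 0.05 and ends "85% power (effect size 0.52), 28 subjects will be required in this cross-over study". Enrolment is expected to be 28 to 32 participants.

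The same paragraph introduces the target in other terms: "This proof of concept study expects to demonstrate a 30% difference in pain reduction between the two intervention sessions".

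Section 2.4.5.2 gives the test for this outcome: "The values will be compared via paired t-test (or Wilcoxon signed-rank test, if data not normally distributed"). Section 2.3.1 makes the number binding, since recruitment continues "until 28 participants have completed both study sessions". The documents state no within-patient correlation, no SD of the paired difference and no one-sided test.

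**The concern.** Sidedness, alpha, effect size, power and number of pairs are tied together: for a paired t-test, fixing any four determines the fifth. The five values printed in section 2.4.7 do not satisfy that relation.

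Two further features of the paragraph make the number hard to interpret. The SD of 2.1 is given for baseline pain across patients and repeated for each session, whereas a paired test depends on the SD of the within-patient difference. And the 30% target does not correspond to the two means that enter the calculation.

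This is the only sample-size justification in the plan, and it sets the recruitment target. If power is nearer 76% than 85%, a non-significant pain comparison is weaker evidence against the concept than the plan implies. A reader who relied on the stated 85% would give it too much weight. The power statement would also be carried into the trial report, where one calculation would show it to be wrong.

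**Working it through.** **Inputs** (section 2.4.7 unless noted): means 5.1 and 4.0; SD 2.1; effect size 0.52; alpha 0.05, two-tailed; power 85%; n = 28; paired t-test (section 2.4.5.2).

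**Effect size.** (5.1 − 4.0)/2.1 = 1.1/2.1 = 0.524, printed as 0.52. The effect size is therefore the mean difference divided by the per-session SD.

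**Formula.** A paired t-test with standardised difference d on n pairs has n − 1 degrees of freedom and noncentrality d√n. Two-tailed power is the probability that a noncentral t variable falls outside ± the 97.5th percentile of t. For a one-tailed test it is the probability of exceeding the 95th percentile.

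**Reproducing the plan's figure.** With d = 0.52 and n = 28, noncentrality is 0.52 × √28 = 2.75 on 27 degrees of freedom.

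| Calculation | Critical t (27 df) | Power at n = 28 | n for 85% |
|---|---|---|---|
| Two-tailed, d = 0.52 | 2.052 | 75.6% | 35.2, so 36 |
| Two-tailed, d = 1.1/2.1 | 2.052 | 76.2% | 35 |
| One-tailed, d = 0.52 | 1.703 | 85.0% | 27.99, so 28 |

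The one-tailed row returns both the stated power and the stated n. Other two-tailed routes at the same effect size do not:

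- The normal approximation, ((1.960 + 1.036)/0.52)², gives 33.2 pairs, and power of 78.6% at 28.
- The Wilcoxon signed-rank test, with relative efficiency 0.955, gives 73.5%.
- The two-sample formula (1.1 points, SD 2.1) gives 66 per arm.
- If all 32 possible enrolees completed, power would be 81.3%.

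**Detectable difference.** For 85% two-tailed power with 28 pairs, d must be 0.587. At a difference SD of 2.1 that is 0.587 × 2.1 = 1.23 points.

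**Dependence on the correlation.** If each session has SD 2.1 and the between-session correlation is ρ, the SD of the difference is 2.1 × √(2(1 − ρ)). This equals 2.1 only at ρ = 0.5. The documents give no ρ, so the table below shows a range, for a 1.1-point difference, 28 pairs and a two-tailed test:

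| ρ (assumed) | SD of difference | d | Power |
|---|---|---|---|
| 0.3 | 2.48 | 0.443 | 62% |
| 0.4 | 2.30 | 0.478 | 68% |
| 0.5 | 2.10 | 0.524 | 76% |
| 0.6 | 1.88 | 0.586 | 85% |
| 0.7 | 1.63 | 0.676 | 93% |

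For exactly 85%, the SD of the difference must be 1.1/0.587 = 1.87, so ρ = 1 − 1.87²/(2 × 2.1²) = 0.60.

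**The 30% target.** The difference used is 1.1 points. Relative to ondansetron with placebo it is 1.1/5.1 = 21.6%. As a share of baseline it is 1.1/6.3 = 17.5 percentage points. Pain 30% below 5.1 would be 5.1 × 0.7 = 3.57, a difference of 1.53 points and d = 1.53/2.1 = 0.73, for which 28 pairs give 96% power. Neither reading of the 30% leads to 5.1 against 4.0 or to an effect size of 0.52.

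**The case against.** The strongest reply is that 0.52 is not a paired effect size at all. The plan attaches 2.1 to pain in each session, so 0.52 can be read as a difference standardised by the per-session SD. On that reading power depends on the between-session correlation, and at about 0.60 the stated 85% two-tailed power is met with 28 pairs. The reply is sound as statistics, and it qualifies any claim that 85% is attainable only with a one-tailed test: that holds when 0.52 is taken as the effect size of the paired test, as the plan presents it. It does not rescue the text, because no correlation or difference SD is given. Either the power is about 76%, or an assumption on which the result depends is missing.

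It is also fair that a one-tailed setting is an inference. The exact match makes it likely but does not prove it, and the inconsistency stands whatever its cause.

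Finally, the outcome is secondary, the primary objectives are pharmacokinetics and tolerability, and this is a proof-of-concept study. The error does not touch the primary analysis, the type I error or participant safety. That limits the consequences, but it does not make the statement correct. The mismatch over 30% is a separate wording fault and adds nothing to the power error itself.

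**Conclusion.** The concern holds: the power statement is wrong as written. Taking 0.52 as the paired effect size, with a two-tailed alpha of 0.05 and 28 pairs, power is 75.6% (76.2% with the unrounded 1.1/2.1), about nine percentage points below the stated 85%. The chance of missing the planned effect is about 24% rather than 15%, and 85% power would need 36 pairs (35 unrounded).

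These figures assume a difference SD of 2.1, that is, equal session SDs of 2.1 and a correlation of 0.5. A correlation near 0.60 would restore 85%; a lower one would reduce power further, to 62% at 0.3. The 30% target is inconsistent with the means used. Because this paragraph is the plan's only basis for its sample size, it must be corrected even though the outcome is secondary.

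**What to change.** Rewrite the sample-size paragraph in section 2.4.7:

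- **Power.** Keep 28 and state that 28 evaluable participants give about 76% power (paired t-test, two-tailed alpha 0.05) for a 1.1-point difference when the SD of the within-patient difference is 2.1. Alternatively, state that 28 give 85% power for a difference of 1.23 points at that SD.
- **SD.** Say explicitly that 2.1 is being used as the SD of the within-patient difference. If the sponsor has data supporting a smaller difference SD, or a correlation of about 0.60, state and justify it, and recompute the power from it.
- **Target.** Replace the 30% with the difference actually used: 1.1 points, which is 22% of 5.1 or 17.5 percentage points of the 6.3 baseline.

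The cost is one paragraph and, unless a smaller difference SD is justified, a less favourable power figure. No participants, visits or analyses change.
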